## 2 Introduction, Background Information and Scientific Rationale

### 2.1 *Background Information and Relevant Literature*

Gastrointestinal hemorrhage is the 19th most common diagnosis for hospital admissions. A total of 86 % of patients with gastrointestinal hemorrhage are admitted to the hospital. However, when esophagoduodenoscopy is performed in the emergency department (ED), 30 % to 46 % of ED patients with acute UGIBs can be safely discharged. Risk stratification in the ED presents a logistic issue because gastroenterologists are frequently unavailable to conduct ED-based esophagoduodenoscopies. As a result, many patients with benign diseases are admitted to the hospital only to have a negative endoscopy result (Meltzer AC et al., 2013). The HemoPill has the potential to provide information on the presence or absence of blood in the GI-lumen which is a valuable information on the urgency of a situation if viewed in the general clinical context of a given patient. The HemoPill is a CE-marketed device and has been on the European market since 2019. Since market entry, the following literature on the use of the HemoPill has been published:

### **Telemetric capsule-based upper gastrointestinal tract – blood detection – first multicentric experience**

Brunk and colleagues presented results from an observational study on the use of the HemoPill in terms of safety and usability under real-life conditions from experiences in 12 hospitals (Brunk T et al., 2021). The use of the HemoPill in 61 patients was retrospectively analyzed. Indications for HemoPill application were clinical suspicion of UGIB, suspected small bowel bleeding after uneventful esophagoduodenoscopy (EGB) and colonoscopy if symptoms persisted, or exclusion of rebleeding after hemostasis. Primary endpoints were technical success and bleeding detection/exclusion. Secondary endpoints included adverse events and change of clinical course. Complete baseline characteristics were available in 49 of 61 patients (80.3 %). Mean age was 70 ( $\pm$  10.7) years, 41 % were female. Mean hemoglobin level at admission to the emergency department was 8.1 g/dL ( $\pm$  1.6). Over signs of bleeding such as melaena and/or hematochezia were present in 27 patients (55 %). Median Glasgow-Blatchford score (GBS) was 10 (range 0 – 19). 46 patients (94 %) had a GBS > 1. 61 patients received the HemoPill; in 45 patients (74 %), the capsule was administered due to the suspicion of UGIB, in 12 patients (20 %), the capsule was used for detection of a suspected small intestinal bleeding and in 4 patients (7 %), HemoPill was used as a “second look” tool after primary hemostasis in the upper GI-tract. One patient was excluded as data transfer was stopped after 10 minutes of recording. Of the remaining 60 patients, 35 (58 %) had a positive capsule signal while 25 (42 %) had a negative HemoPill result. In 20 of 35 patients (57 %) with a positive HemoPill signal, evidence of bleeding was seen in a subsequent endoscopic work up. The bleeding sources were angiodysplasia (n = 10), peptic ulcer (n = 5), Dieulafoy lesion (n = 1), esophageal varices (n = 1), esophagitis (n = 1), erosive gastritis (n = 1), unknown as only blood was seen (n = 1). In 15 of 35 patients with a positive HemoPill signal, no bleeding source was detected, yet only in 11 of these 15 patients an EGD was performed.

In 20 of 25 HemoPill negative patients, endoscopy was performed and did not reveal a bleeding source or blood/hematin. Until discharge, no clinically relevant bleeding was detected in HemoPill negative patients.

The authors state that all endoscopically confirmed bleedings had been detected by the HemoPill and no HemoPill negative patients showed an endoscopically or clinically proven bleeding site. In HemoPill negative patients (25 / 60), the further clinical course was changed in 18 cases (72 %). Change from urgent to elective regarding timing of endoscopy was reported in 40 % of cases (10 / 25). Small bowel enteroscopy was avoided in 5 / 25 patients (20 %) and EGD was avoided in 3 / 25 patients (12 %). In 7 / 25 patients, no change of the clinical course occurred. Brunk T et al. conclude that HemoPill is a promising tool for real-time blood detection to aid stratification of patients with UGIB (Brunk T et al., 2021).

#### **2.1.1 Study importance**

As described in the above-mentioned publications, further tools for risk stratification in patients with suspected UGIB are in demand to identify high risk patients and adequately allocate resources. The clinical data on the use of the HemoPill in Europe is generally positive and promising. As Brunk T et al. conclude, thus far no HemoPill negative patient developed a clinically significant GI bleeding until discharge and every endoscopically confirmed bleeding pathology was associated with a previously positive HemoPill measurement. The proposed study further investigates the safety and performance profile of the HemoPill by controlling and limiting latency to endoscopy. HemoPill may prove to be a valuable tool for the US healthcare system by reliably providing information on the presence or absence of blood in the GI tract. HemoPill does not require patient preparation and measurement data is displayed in a way that allows for immediate, real-time interpretation. Thus far, HemoPill has a high technical success rate and is well tolerated by patients. Only patients who are already scheduled for endoscopy for suspected UGIB are eligible for participation in the study and endoscopy is neither delayed nor prolonged by the study protocol. The potential benefits for the US healthcare system are already highlighted in publications describing the use of the subject device in Europe.

#### **2.2 Name and Description of the Investigational Agent**

The investigational device is the HemoPill, consisting of an ingestible capsule (HemoPill acute), and a wireless data receiver module (HemoPill Receiver) that displays and stores data.

### 2.2.1 HemoPill acute capsule

The HemoPill acute is an active medical device. It is a wireless, battery-powered ingestible capsule containing an optical sensor, electronics, radio link and software. The electronic assembly (as a stack of three electronic boards) contains software for measurement data acquisition and signal transmissions. These components are encapsulated into a transparent epoxy resin that is coated with Parylene C.

The signals of the HemoPill acute sensor correlate with the presence of blood in the measuring slot of the capsule and are transmitted wirelessly to the HemoPill Receiver.

[figure not shown]

Figure 1: Components of the HemoPill acute

[figure not shown]

Figure 2: Dimensions of the HemoPill acute

The operating mode of the optical sensor is based on alternating screening of the measuring slot using wavelength of 415 nm (violet) and 700 nm (red). The optical sensor measures the absorption of light by the medium inside the measuring slot for each wavelength separately. The ratio of red to violet light intensity, that has not been absorbed is, calculated. Measurement data is transmitted by radio to the HemoPill Receiver. A more detailed description is provided in chapter 2.1.2.

The HemoPill acute is activated by exposing the activation area to light. The light intensity required for activation is higher than normal environmental light (day light or room light), therefore the exposure to a light-source at close distance is required. The HemoPill Receiver includes a light source for activating the HemoPill acute. The procedure of capsule activation using the activation light source of the HemoPill Receiver is shown in Figure 2-3. In order to ensure sterility, the capsule remains in the blister packaging for activation.

After activation, the capsule conducts one measurement approximately every twelve seconds for at least nine hours. Subsequently, the device changes into a second mode to facilitate monitoring the presence of the device in the patient using the HemoPill Receiver. During this second period, no measurements are conducted, but data packages are transmitted until at least 21 days after activation.

[figure not shown]

Figure 3: Blister package of HemoPill acute (activation area is marked by triangle, (1) and (2))

Table 1: Specifications of the HemoPill acute

Dimensions and weight			
Product dimensions	26.3 mm x 7.0 mm		
Weight	Approx. 2 g		
Energy source			
Battery type	Silver oxide		
Version			
Software version	02.xx.yy		
Electronics version	01.xx.xx		
CAD version	12		
Wireless specification			
Frequency range	433.05 MHz to 434.79 MHz		
Send frequency	434.42 MHz		
Send bandwidth	100 kHz		
Send rate	0.083Hz		
Transmission period	< 10ms		
Modulation	GFSK		
ERP	-24 dBm		
Range	Short range		
Application related specifications			
General specifications	Single use		
	EO sterilized		
	Latex-free		
Shelf life	21 months		
Technical characteristics			
General characteristics	Unidirectional data transmission		
	MR conditional		
Environmental conditions for operation, transport and storage			
	Operation	Storage	Transport
Temperature	+20 °C to +40 °C	+10 °C to +30 °C	-10 °C to +50 °C
Relative humidity	20% to 90% RH; non-condensing	20% to 85% RH; non-condensing	20% to 90% RH; non-condensing
Air pressure	785 to 1060 hPa	700 to 1060 hPa	700 to 1060 hPa
Max. operating height	≤ 2000 m	-	-

### 2.1.1.1 HemoPill Receiver

The HemoPill Receiver (Figure 2-4) is an accessory (wireless, handheld device) to the HemoPill acute. The HemoPill acute and the HemoPill Receiver can only be used together. The HemoPill Receiver is designed to receive data from the HemoPill acute via the radio link and display this data to the user.

[figure not shown]

Figure 4: Components of the HemoPill Receiver

The HemoPill Receiver features and is operated by a touch-sensitive color display. After activation of the HemoPill Receiver using the power button, the user controls the device via the touch display. Furthermore, the HemoPill Receiver features an USB-interface to connect to the HemoPill Printer for printing measurement results for documentation, a LED light source for activation of the HemoPill acute, and an indicator LED for data reception and charge level of the internal secondary battery (Figure 2-4). The internal secondary battery can be charged via the DC connection using the supplied external power supply (Figure 2-5). Normal operation of the device is possible also during battery charging. The Receiver power supply is included in the scope of delivery.

The HemoPill Receiver contains a software for displaying the values measured and transmitted by the HemoPill acute. The HemoPill Receiver receives and saves the measured values. The values are displayed numerically and as a curve diagram on the display of the HemoPill Receiver.

The HemoPill receiver can be disinfected using alcohol-based cleaning agents and disinfectants.

[figure not shown]

Figure 5: Connecting the HemoPill Receiver to the power supply

Table 2: Specifications of the HemoPill Receiver

Dimensions and weight			
Product dimensions (W x H x D)		96 x 145 x 37 mm	
Net weight		262 g	
Packaging information/dimensions (W x H x D)		Case 465 x 350 x 110 mm	
Gross weight		approx. 4.4 kg (including accessories and packaging)	
Version			
Software version		02.xx.yy	
Device version		1.xx	
Receiver power supply			
Power input		100 V – 240 V AC	
Supply voltage		220 V – 240 V AC	
Max. power consumption		5 W / 12 VA 5 W / 16 VA	
Supply frequency		50/60 Hz	
DC output voltage		5 V	
Max. output current		5 A	
Overcurrent protection (power input)		2 A	
Wireless specification			
Operational Frequency band		433.05 MHz to 434.79 MHz	
Reception frequency		434.42 MHz	
Reception bandwidth		100 kHz	
Modulation		GFSK	
Receiver category		2	
Application related specifications			
General specifications		Reusable	
		Non-sterile	
Environmental conditions for operation, transport and storage			
	Operation	Storage	Transport
Temperature	+10 °C to +40 °C	+10 °C to +40 °C	-10 °C to +50 °C
Relative humidity	20% to 80% RH; non-condensing	20% to 90% RH; non-condensing	20% to 90% RH; non-condensing
Air pressure	785 to 1060 hPa	700 to 1060 hPa	700 to 1060 hPa
Max. operating height	≤ 2000 m	-	-

### 2.1.1.2 HemoPill Printer

The HemoPill Printer serves to document values measured by the HemoPill Receiver. It is designed solely for use with the HemoPill Receiver. It may only be connected to the HemoPill Receiver using the USB cable supplied. The accessories of the HemoPill Printer furthermore contain the power supply (rated output: 9.0 VDC, 4A) as well as the paper reels for the printer.

HemoPill printer is not a medical device. It must not be used in the patient environment.

Figure 6: HemoPill printer

### 2.1.2 Operating principle

The HemoPill acute has been specifically developed for detection of blood. The operating principle of the HemoPill acute relies on an optical sensor for alternating screening of the measuring gap in two different wavelengths emitted from LEDs (bicolor) on the other side of the measuring gap, opposite the sensor: red light at 700 nm and violet light at 415 nm (Figure 2-8). The optical sensor measures separately transmitted light intensity that passes the measuring gap, and the ratio of red to violet light transmission is calculated. The intensity of the measured light depends on the absorption characteristics of the medium in the measuring gap (e.g. blood). The measurement data is transmitted to the HemoPill Receiver via a radio link at a frequency of 434.42 MHz.

[figure not shown]

Figure 7: Sensor principle; A: Red and violet light source, B: sensor/measuring gap, C: Light sensor

[figure not shown]

Figure 8: Sensor principle (side view)

#### 2.1.2.1 Sensor principle

The transmission effects depend on the respective digestive tract content in the measuring gap. The two wavelengths being emitted by the bicolor LED have been selected to create a high sensitivity of the sensor

to the presence of blood inside the measuring gap. Blood shows a minimum light transmission rate (maximum light absorption rate) around 415 nm, and a maximum light transmission rate (minimum light absorption rate) around 700 nm (from about 650 nm into the infrared-range). These two wavelengths have been selected for the bicolor LED. Undiluted blood (venous, arterial) or hematin absorbs violet light at 415 nm approx. 1,000-times more strongly than red light at 700 nm. The light sensor has a comparable sensitivity at both of these wavelengths.

The sensor operation follows a fixed sequence:

- First, the red LED (700 nm) is activated, and the resulting voltage signal at the light sensor, indicating the grade of absorption of red light, is digitalized ( $I_{red}$ ) and stored. The red LED is deactivated subsequently.
- Second, the violet LED (415 nm) is activated, and the resulting voltage signal at the light sensor, indicating the grade of absorption of violet light, is digitalized ( $I_{vio}$ ) and stored. The violet LED is deactivated subsequently.
- Third, the sensor value  $Q$  is calculated on the board of the HemoPill acute capsule and transmitted to the HemoPill Receiver via radio link.

### 2.1.2.2 Sensor value calculation

The light sensor is translating the light intensity into a voltage, which is digitalized with a resolution of 10 bit. Therefore, the intensities  $I_{red}$  and  $I_{vio}$  are given as an integer value on a scale from 0 to 1023.

The actual sensor value  $Q$  is calculated on the basis of these intensity values and further a correction factor for compensation of gain and offset errors of the intensity measurement. The correction factor is determined during production for each HemoPill acute capsule individually and stored in the non-volatile memory of the capsules. The correction factors are  $K$  for the gain error, and  $I_{leak,red}$  and  $I_{leak,vio}$  for the offset errors of the two LED wavelengths.

A gain error can be caused by e.g. variances in the characteristics curves of the LEDs, the resistors or the voltage supply of the HemoPill acute capsule as well as variance of the surface structure of the encapsulation in the area of the measuring gap. An offset error can be caused by variances in the gap manufacturing that might allow light to reach the light sensor without passing the measuring gap, e.g. if the depth of the gap does not reach the printed circuit board (PCB) which is covered by a light blocking layer.

The sensor value  $Q$  determines the ratio between the grade of absorption of violet light and the grade of absorption of red light by the medium or fluid within the measuring gap. For example, if the absorption of violet light is ten times higher than the grade of absorption of the red light, the sensor value  $Q$  is 10. A detailed description of the calculation method is given in the document “002\_OVE\_HP\_Quotient calculation\_Rev03\_2018-04-06” in Volume 002.

$$Q = I_{corr2,red} / I_{corr2,vio}$$

On the display of the HemoPill receiver the HI-value (short for HemoPill Indicator) is presented to the user. The sensor value  $Q$  is not appropriate for usability reasons, as the quotient requires a logarithmic scale to be read and interpreted in a way that it is clinically useful. Therefore, the HI-value, which ranges between 0 and 1.5 on a linear scale, is used. It is calculated as follows:

$$HI = 0.5 \times \log_{10}(Q)$$

The resulting decimal values are rounded down to have one decimal number (e.g.  $0.88 = 0.8$ ,  $1.31 = 1.3$ ). by rounding down, the HI-value has the same clinical significance as the quotient (e.g. a quotient of  $Q = 99$  corresponds to a HI-value of  $HI = 0.9$ , therefore both are not crossing 100 and 1.0, respectively).

If the measuring gap is filled with blood, violet light can be almost completely blocked, while red light passes through the sensor gap almost entirely unimpeded. In this case, the HI-value can reach its maximum of 1.5.

Other foodstuffs can return a HI-value of up to 0.7 in individual cases. In empty stomachs the sensor can come into contact with undiluted bile as it passes through the stomach passage. This can lead to a HI-value of approx. 1.0. Several substances have been tested in an animal study, see Volume 005.

### 2.1.3 Clinical application

For intended examination, the detection of blood in the upper gastrointestinal tract, the patient swallows the HemoPill acute capsule (after activation) ((1) in Figure 2-9). The capsule must be taken with at least 100 ml water, which aids swallowing and promotes the suspension of blood. The HemoPill acute continuously sends measurement data which are received and recorded by the HemoPill Receiver ((2) in Figure 2-9). Measurement data are displayed on the HemoPill Receiver for interpretation by the user ((3) in Figure 2-9). After the data acquisition procedure, the data can be printed using the HemoPill Printer.

[figure not shown]

Figure 9: Operation principle of the HemoPill acute system

The HemoPill acute continuously send approx. 5 measured values per minute to the HemoPill Receiver. The duration of the measurement is approx. 9 hours from activation of the HemoPill acute. The values measured by the capsule are displayed numerically and as a curve diagram on the display of the HemoPill Receiver (Figure 2-10). Furthermore, the capsule ID, which is individual for each individual capsule, is shown on the display, ensuring an allocation to the patient. The capsule ID is indicated directly on the blister packaging of the capsule. The separately enclosed patient labels (four stickers) serve the document in the patient file and do also include the capsule ID.

The numerical display shows the maximum HI value ( $^{MAX}HI$ ) (see (1) in Figure 2-10) and the last measured value ( $^{LAST}HI$ ) (see (2) in Figure 2-10)). The respective measuring time is located below.  $^{LAST}HI$  is updated with each measured value received (about 5 times per minute).  $^{MAX}HI$  updates every minute during the first hour, after the first hour until the 9th hour about every 8 minutes. The  $^{MAX}HI$  value is also plotted as a curve over time (Figure 2-10). By pressing the information button (see (3) in Figure 2-10) information on interpreting the HI values are shown.

[figure not shown]

Figure 10: Information on the display of the HemoPill Receiver

For interpretation of the HI values the following procedure is recommended:

1. First, interpret the maximum HI value within 10 minutes from swallowing the HemoPill acute, see Table 3.
2. Then interpret, independently of this, the maximum HI value in the further course of the measurement ( $\geq 10$  minutes after swallowing), see Table 4.

Table 3: Interpretation of the HI value within 10 minutes after swallowing

HI	Within 10 minutes after swallowing
$< 0.8$	
Negative            Liquid blood (or hematin) was not detected.            NOTE: Blood may still be present but may be highly diluted or exist in unsuspended, adherent coagula.

$\geq 0.8$	
Positive            Liquid blood (or hematin) was detected.

Table 4: Interpretation of the HI value  $\geq 10$  minutes after swallowing

HI	$> 10$ minutes after swallowing
$< 1.0$	
Negative            Liquid blood (or hematin) was not detected.            NOTE: Blood may still be present but may be highly diluted or exist in an unsuspended, adherent coagula.

$\geq 1.0$	
Positive            Liquid blood (or hematin) was detected.

The HemoPill is excreted through being passed naturally by the patient. To check that this has occurred, the transmission function of the capsule is active for at least 21 days.

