Description of Agent/Procedure	
HemoPill acute:  A capsule equipped with a photometric sensor for the detection of blood or hematin in the gastrointestinal tract. The capsule can be ingested and travels through the gastrointestinal tract naturally. For approximately 9 hours, the photometric sensor measures the absorption of light at specific wavelengths through the contents of the gastrointestinal lumen. Blood and hematin have a specific absorption behavior for the defined wavelengths used. The HemoPill acute capsule makes a measurement every 12 seconds and wirelessly transmits data to the HemoPill Receiver that displays the HemoPill acute data.
 
HemoPill Receiver:  Handheld device that displays HemoPill acute data. The HemoPill Receiver displays the data in a graphical form as well as the current value and the highest measured value. The threshold value for confirmation of presence of blood or hematin is displayed for reference.
		
Reference Therapy	Endoscopy		
Key Procedures	
Diagnostic procedures used leading to a suspicion of UGIB are not within the scope of this trial as these procedures are necessary irrespective of trial participation. A suspicion of UGIB, however justified, is a prerequisite for trial participation.
 
Endoscopy and associated procedural steps are omitted as endoscopy is scheduled for trial participants irrespective of trial participation.
		
Statistical Analysis	
Provide patient information and obtain informed consent. Screen by inclusion and exclusion criteria, document.
 
Activation of the HemoPill acute by the investigator as per instructions for use.
 
Ingestion of HemoPill acute capsule by the trial participant with a minimal amount of water.
 
Data collection on the HemoPill Receiver from ingestion of the HemoPill acute capsule until conclusion of endoscopy.
		
	
Relation between HemoPill acute measurements and endoscopic findings along the lines of the following definitions for “true positive”, “true negative”, “false positive”, “false negative”:
 
 
 True Positive	HemoPill acute measurement indicates presence of blood; Endoscopy identifies fresh blood or hematin in the GI lumen.	
 
	True Positive	HemoPill acute measurement indicates presence of blood; Endoscopy identifies fresh blood or hematin in the GI lumen.

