## 4 Study Design and Endpoints

### 4.1 Description of Study Design

Patients are included according to the defined inclusion criteria and prepared for endoscopy. At the latest possible time before endoscopy, a HemoPill acute capsule is administered with a minimal amount of water. The HemoPill receiver is stored in a carrying bag. The transparent part of the bag over the display of the receiver is covered with tape. The LED light is left uncovered, so a successful signal transmission can be checked at any times. The investigator is unaware of the HemoPill acute measurement result until endoscopy has concluded. After a latency of minimum 20 minutes, maximum 60 minutes, endoscopy is performed as scheduled, identifying blood within the GI lumen, if present. A minimum latency is introduced to ensure HemoPill acute is able to make a measurement without interference from endoscopy, e.g., insufflation or endoscopic light.

The amount of blood identified in endoscopy is visually analyzed and pictures are taken. For the estimation of the amount of blood present in a patient, comparative images are provided. Assessment categories are:  $x < 20$  mL and  $x > 20$  mL. The detection threshold is introduced to provide a point of reference for the HemoPill acute detection rate.

Pathologies, if found, are treated as per clinical standard. HemoPill acute measurements regarding presence or absence of blood are put in relation to endoscopic findings.

Endoscopic images are further analyzed to determine the digestive state of the blood found as HemoPill acute is capable of detecting fresh blood or hematin. Blood digested to a point beyond hematin is no indicator for an acute bleeding pathology. The following foreseeable combination of events are described and allocated to “True Positive”, “False Positive”, “True Negative”, and “False Negative”.

- **True positive:**  
HemoPill acute measurement indicates presence of blood; Endoscopy identifies fresh blood or hematin in the GI lumen
- **False positive:**  
HemoPill acute measurement indicates presence of blood; Endoscopy does not identify fresh blood or hematin in the GI lumen.
- **True negative:**  
HemoPill acute measurement does not indicate presence of blood; Endoscopy does not identify fresh blood or hematin in the GI lumen in quantities  $> 20$  mL; Minimum latency of 20 minutes achieved.
- **False negative:**  

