#### **6.1.4 Preparation**

##### Subject device

In the following the stepwise clinical use of the HemoPill acute is described

- Switching on the HemoPill Receiver
- Activation of the HemoPill acute using the HemoPill Receiver
- Establishment of a data connection between HemoPill acute and HemoPill Receiver
- Handing the activated HemoPill acute to the patient in the blister
- Swallowing of the HemoPill acute with a small amount of water

- Receiving and reading of measurement data (HI values) using the HemoPill Receiver
- Interpretation of the measured values by the user based on the information provided in the IFUs of the HemoPill acute and HemoPill Receiver (document A01)
- At the end of measurement, deactivation of the data connection with the HemoPill Receiver
- Natural excretion of the HemoPill acute by the patient

A detailed description on the handling of the HemoPill Receiver can be found in the respective instructions for use, provided as a separate document.

Control product

The control procedure is endoscopy. Endoscopes and associated devices and accessories are chosen as per site protocol, physician's discretion and provided by NYU. Use of endoscopy is clinically established, as are requirements for preparation.

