**6.1.5 Dosing and Administration**

Subject device

The HemoPill acute capsule is switched on using the HemoPill Receiver as described in the instructions for use. A data connection between the HemoPill acute capsule and the HemoPill Receiver is established. Every trial participant receives a single, sterile, switched on HemoPill acute capsule for ingestion with a minimal amount of water. The HemoPill acute capsule is not to be chewed. Ingestions is timed under consideration of endoscopy scheduling. Minimum latency to endoscopy should be 20 minutes, maximum latency to endoscopy should be one hour. The HemoPill Receiver is operated by the investigators.

Control product

Application of endoscopy as per clinical standard. Scheduling of endoscopy follows NYU protocol and suspected urgency of a given patient's situation.

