#### 6.3.1 Administration of Procedural Intervention

The investigator activates the HemoPill acute capsule by using the HemoPill Receiver. A data connection to the HemoPill Receiver is established. The activated HemoPill acute, still within the blister, is handed to the trial participant for ingestion with a minimal amount of water. Ingestion is timed under consideration of the previously established scheduling for endoscopy. Between HemoPill acute ingestion and start of

endoscopy, a minimum of 20 minutes should have elapsed. No more than 60 minutes between HemoPill acute ingestion and start of endoscopy should elapse. A trial participant is subjected to one intervention.

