## 7.2.2 Enrollment

If a patient is successfully screened and informed consent obtained, he or she is enrolled into the trial. As endoscopy is already scheduled, a trial participant likely stays at the hospital. Approximately 20 to 60 minutes prior to endoscopy, the HemoPill acute capsule is activated by the investigator and a data connection to the HemoPill Receiver is established. Then, the HemoPill acute capsule is ingested by the trial participant with a minimal amount of water.

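### The device description requires at least 100 ml of water with the capsule, but all six trial instructions say a minimal or small amount, with no figure and no reason

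*Combined protocol and SAP*

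**What the plan says.** Section 2.1.3 (Clinical application) describes use of the capsule to detect blood in the upper gastrointestinal tract. It makes the water volume mandatory and gives a measurement reason as well as a swallowing reason: "The capsule must be taken with at least 100 ml water, which aids swallowing and promotes the suspension of blood".

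The trial procedure is worded differently in every place where water is mentioned:

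- Protocol Summary: "Ingestion of HemoPill acute capsule by the trial participant with a minimal amount of water"
- 4.1: "a HemoPill acute capsule is administered with a minimal amount of water"
- 6.1.4: "Swallowing of the HemoPill acute with a small amount of water"
- 6.1.5: "switched on HemoPill acute capsule for ingestion with a minimal amount of water"
- 6.3.1: "is handed to the trial participant for ingestion with a minimal amount of water"
- 7.2.2: "the HemoPill acute capsule is ingested by the trial participant with a minimal amount of water"

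On what a negative reading means, the note to Table 3 in section 2.1.3 says: "Blood may still be present but may be highly diluted or exist in unsuspended, adherent coagula".

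**The concern.** The primary endpoint is the agreement of the capsule's positive or negative reading with endoscopy (4.2.1, 10.4.2). By the protocol's own account, water helps suspend blood, and blood that is not suspended can be missed. Water volume is therefore a condition of the test, like the 20 to 60 minute latency, which the protocol does control.

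Two things are at stake. First, the six instructions leave the volume to whoever hands over the capsule. It may fall below the stated requirement or differ between patients. Second, section 15.1 says the data are meant to help users interpret a measurement. If users are told to give at least 100 ml and the trial gave an unrecorded smaller amount, the reported accuracy, sensitivity and specificity describe a different test condition.

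The plan has no safeguard that would reveal this. Section 6.3.3 marks compliance assessment as not applicable. Section 10.4.5 checks only that the capsule was taken. Sections 10.4.8 and 10.4.9.2 plan no demographic subgroup analyses and no exploratory analyses.

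**Working it through.** No sample size or error rate enters this point, so the main check is a comparison of texts.

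**Count of instructions**

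| Place | Amount of water | Figure | Reason | Reference to 2.1.3 |
|---|---|---|---|---|
| 2.1.3 (device description) | at least 100 ml, mandatory | yes | yes | – |
| Protocol Summary | minimal | no | no | no |
| 4.1 | minimal | no | no | no |
| 6.1.4 | small | no | no | no |
| 6.1.5 | minimal | no | no | no |
| 6.3.1 | minimal | no | no | no |
| 7.2.2 | minimal | no | no | no |

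There are six trial instructions: five say minimal, one says small, and none states a volume. The 100 ml figure appears once, in 2.1.3.

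**Can the two be reconciled?** Minimal might be shorthand for the required minimum. The word small in 6.1.4, and the lack of any figure or cross-reference, make that reading weak. The Protocol Summary and 6.1.5 point to the instructions for use for activating the capsule, and 6.1.4 does so for interpreting the readings. None of them does so for the water.

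**Would 100 ml dilute the blood too far?** This is a rough check on the proposed fix, not an estimate of bias. It assumes full mixing and no other gastric fluid.

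- 20 mL of blood (the threshold in 4.1) in 100 ml of water: 20 / (20 + 100) = 16.7%.
- The bench solution in Table 7 was weaker, at 6.25%, and gave a mean maximum quotient of 423.
- With the formula in 2.1.2.2, HI = 0.5 × log10(423) = 1.31, shown as 1.3 after rounding down. This is above both cut-offs in Tables 3 and 4 (0.8 and 1.0).
- Diluting 20 mL to 6.25% takes 20 / 0.0625 = 320 ml in total, that is 300 ml of added fluid.

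Under these assumptions, 100 ml leaves 20 mL of blood more concentrated than the bench solution. The 423 is an average. The bench pass mark was a quotient of only 41, which gives 0.5 × log10(41) = 0.81, shown as 0.8. That reaches the early cut-off but not the later one. Mixing and residual fluid in patients are unknown.

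**Why no shift in accuracy is computed.** Less water could mean less suspension or less dilution, so even the sign is open. A fixed shift per patient would also be wrong under the definitions in 4.1. A patient with less than 20 mL of blood counts as correct either way: a positive reading is a true positive, and a negative reading is a true negative once the 20-minute latency is met.

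**The case against.** The strongest reply is that 2.1.3 is background on general device use, while sections 4, 6 and 7 govern the trial and agree with each other. On that view there is one instruction repeated, not six contradictions, and it may be deliberate. Section 4.1 asks for ingestion as late as possible before endoscopy, patients are sedated (10.6.1), and extra fluid could disturb the visual estimate of blood volume. The volume might also be set in documents not available to this review: the instructions for use, training material, Manual of Procedures, CRF, or the parts of the protocol missing from the public text. Table 3 speaks of adherent clots, and nothing shows that 100 ml would free them. The earlier clinical, volunteer and animal results, as described, state no water volume, so nothing shows that they depended on one.

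Much of this is fair. A deliberate choice is plausible, the effect is unproven, and the unseen documents could settle the matter. It is also true that a bare minimum of 100 ml would still let volumes vary upwards. But the conflict in the text remains. Section 2.1.3 gives conditions for the very task the trial tests, nothing exempts the trial from them, and no reason for a smaller volume is given.

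**Conclusion.** The concern holds. Followed as written, the trial instructions allow the index test to be run outside the condition the same protocol calls mandatory, at an unspecified volume, and the plan provides no compliance check on it. This should be corrected because it concerns how the primary measurement is made.

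The size of any effect on accuracy, sensitivity, specificity or power cannot be derived from the documents, and neither can its direction. The conclusion rests on the text available. It would shrink to a wording correction if minimal was meant to be 100 ml, or if a document not seen here fixes the volume.

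**What to change.** Choose one of two courses and use the same wording in all six places (Protocol Summary, 4.1, 6.1.4, 6.1.5, 6.3.1, 7.2.2):

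1. Require at least 100 ml, as in 2.1.3, after a clinical check that this is acceptable 20 to 60 minutes before sedated endoscopy.
2. If less is needed because of sedation or the image-based blood estimate, state one fixed volume and the reason, and limit the accuracy conclusion to that way of giving the capsule.

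Either way, record the volume each patient takes, unless the CRF already does. The choice belongs to the sponsor and the investigator.

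The cost is protocol wording, at most one data field, the clinical check for the first course, and a narrower conclusion for the second.
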